5.3 RANDOMIZATION AND BLINDING

This study is randomized, double-blind, and sham-controlled to minimize bias. Subjects will be randomized following the post-washout baseline assessment (Day 0) to one of the two treatment groups (sTMS vs. sham treatment), at a 1:1 ratio. Randomization will be stratified by site in blocks of 10 determined by a computer generated randomization table defined prior to the start of the trial. Each site will be given a set of 10 randomized PPMs. The assignment is determined by a computer generated randomization table defined prior to the start of the trial. Each Patient Passport Module (PPM) has a 128-bit number preprogrammed for use with a corresponding active or sham device. This number is independent of the Subject ID or device serial number, and is not shown on the PPM or displayed by the device. It is impossible to determine if the PPM is to be used with an active or sham device just by looking at the number. Instead, the software embedded in the device reads the number and uses a decoding algorithm to determine if the PPM is to be used with that particular device. If not, the device will inform the user that the PPM is not valid for that device. The decoding algorithm is kept with the manufacturer, and is not known by the clinical site or any clinical monitor.

These PPMs are labeled with a sequential number to maintain the blinding. At the time an individual subject is randomized, the site will select the next PPM in the instructed numerical order and assign it to that subject. Each site will keep a log of the PPM number assigned to each subject. (See Section 6 for additional information on the PPM). Investigators who perform the assessments, those administering treatment, and subjects who participate in the trial will be blinded to study treatment. A Treatment Blinding Questionnaire will be completed by those performing the assessments, those administering treatment, and subjects at the Week 1 and Week 6 Evaluation Visits for sponsor review to ensure the blind is maintained.

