- Submission of knowingly false information from the research facility to the Sponsor, study monitor, or appropriate regulatory authority.

Subjects who withdraw from the study for any reason will not be replaced. Subjects who voluntarily withdraw from the study will be asked to complete the Week 6/Early Termination assessments. Subjects who are withdrawn due to adverse events will be followed until resolution or stabilization of the adverse event.

SAMPLE SIZE

The primary endpoint of the study is clinical response at Week 6, defined by 50% or greater reduction on the Hamilton Rating Scale for Depression (HAM-D¹⁷) from baseline (Day 0). The null and alternative hypotheses of interest are:

$$H_0: \pi_A - \pi_S = 0$$

vs.

$$H_a: \pi_A - \pi_S \neq 0$$

where π_A is the proportion of subjects who show 50% or greater improvement in HAM-D¹⁷ total score from baseline (Day 0) to Week 6 for the active sTMS treatment and π_S is the equivalent value for the sham-controlled group.

The calculation of sample size requirements for this confirmatory study is based on the results observed in the per-protocol (PP) analysis of non-treatment-naïve subjects who completed Week

6 HAM-D¹⁷ assessments in the previous NEST trial NND-3001.

In that population, 34% of subjects treated with active sTMS were categorized as responders, whereas only 8% of sham treated subjects responded. Assuming true population response rates of 34% for sTMS and 8% for Sham, power analysis indicates that a PP sample size of 92 subjects (i.e., 92 subjects, or 46 subjects per treatment group, without major protocol violations and with HAM-D¹⁷ measured at Week 6) yields 81% power to demonstrate superiority of sTMS over Sham, where the statistical test is Fisher's exact test at a two-sided 0.05 level of significance.

The sample size ratio for the active treatment group to sham-controlled group is 1:1. Based on a conservative estimate of published studies, approximately 23% of enrolled subjects may not be part of the PP population in each treatment group. Thus, a total of 120 subjects (60 per group) will therefore be enrolled in the study to account for potential drop-outs and protocol noncompliance prior to Week 6.

SCHEDULE OF VISITS

Table A on the following page displays the schedule of visits and procedures for protocol NND-3002. Full details can be found in the protocol.

TABLE A: STUDY FLOWCHART

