ACTIVITY	SCREEN	BASELINE (DAY -0)	WK1 TX DAY 5	WK2 TX DAY 10	WK3 TX DAY 15	WK4 TX DAY 20	WK5 TX DAY 25	WK6/ EARLY TERM TX DAY 30	WK7 OPEN LABEL TX DAY 5	WK8 OPEN LABEL TX DAY 10	WK9 OPEN LABEL TX DAY 15	WK 10,11, OPEN LABEL TX DAY 20,25,30
Informed Consent	X											
Inclusion/Exclusion Criteria	X	X										
Mini Mental Status Exam (Version 2)	X											
MINI	X											
ATHQ	X											
Blinding Questionnaire			X					X				
Randomization		X										
NeoSync EEG	X	X										
Med/Psych History	X											
Vital Signs		X						X				
Labs ^a	X											
Pregnancy Test (HCG) ^b	X											
Urine Drug Screen ^b	X											
Weight		X						X				
Physical Exam ^a	X											
Demographics	X											
ECG ^a	X											
HAM-D/MADRS	X	X	X	X	X	X	X	X	X	X	X	X
IDS-SR		X	X	X	X	X	X	X	X	X	X	X
C-SSRS	X	X	X	X	X	X	X	X	X	X	X	X
Concomitant Med ^c	X	X	X	X	X	X	X	X	X	X	X	X
Adverse Events ^a	X	X	X	X	X	X	X	X	X	X	X	X

a Optional

b Must be performed at Screening and may be performed at any subsequent visit at the discretion of the Investigator

c In addition to the assessment visits outlined here, All subjects will have 5 treatment visits per week during treatment period changes in adverse events and concomitant medications should be recorded when made known to the site.

Note: The first treatment session may begin on the same day as baseline visit, after subject meets all criteria and is randomized to a treatment arm.

RANDOMIZATION

This study is randomized, double-blind, and sham-controlled to minimize bias. Subjects will be randomized following the post-washout screening/baseline analysis (Day 0) to one of the two treatment groups (sTMS vs. sham treatment), at a 1:1 ratio stratified by study center. The assignment is determined by a computer-generated randomization table defined prior to the start of the trial.

INITIAL SCREENING/BASELINE VISIT:

Potential study participants will be screened for eligibility per the protocol eligibility criteria. The Screening/Baseline visits may be split into two or more days. After informed consent has been signed and washout from previous medications is complete (when necessary), the following assessments will be performed as part of the subject eligibility assessment:

- MINI (Mini International Neuropsychiatric Interview)
- ATHQ (Antidepressant Treatment History Questionnaire)
- Mini Mental Status Exam (MMSE-2)
- Medical and psychiatric history
- Concomitant medication history
- Adverse Events
- Demographics
- NeoSync EEG

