where π_A is the proportion of subjects who show 50% or greater improvement in mean HAM-D¹⁷ total score from baseline (Day 0) to Week 6 for the active treatment and π_S is the equivalent value for the sham-controlled group. The test of the null hypothesis will be based on Fisher's exact test at a two-sided 0.05 level of significance. In addition, the observed response rates and two-sided 95% confidence intervals of the risk difference between treatments will be presented, calculated using the Wilson method discussed in Newcombe (1998).

An assessment of treatment-by-investigative center interaction on the proportion of clinical responders at Week 6 will be carried out using the Breslow-Day test. Sites with fewer than 10 subjects in the PP group will be pooled with other centers by geographic region prior to carrying out analyses (the same pooled sites will then be used for the analyses on the ITT analysis population). The pooling will be carried out before the blind is broken. A 0.15 level of significance will be used to assess the interaction. A non-significant interaction or an interaction significant but only quantitative in nature will support the pooling of results across study centers for the final analysis.

For the six-week open-label follow-up phase, the proportion of patients with a clinical response at each open-label visit for each double-blind treatment and for both treatments combined will be presented. The proportion of patients with a clinical response at each visit will be compared between double-blind treatment in a similar manner as above. These open-label analyses are

considered exploratory.

INTERIM ANALYSES

Due to uncertainty regarding the expected sham response rate and resulting treatment effect differential, this study will utilize an adaptive design that allows one interim sample size re-estimation after a minimum of 70 subjects have been enrolled and completed 6 weeks of treatment (or dropped out prior to 6 weeks). The pre-specified maximum allowable adjusted sample size following re-estimation will be 240 randomized, or two times the initial planned sample size of 120 enrolled, based on practical resource constraints and the desire to achieve a minimum differential of 12% between active and sham response rates. The re-estimation of sample size will be conducted by an independent biostatistician following a pre-specified plan as described by Mehta and Pocock, 2010 and presented to the independent data monitoring board (DMB).

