Specifically, at the interim stage the conditional power (CP) for obtaining a significant beneficial effect of sTMS over sham with respect to the primary endpoint will be calculated by the independent statistician, using the protocol-specified planned sample size of 92 *evaluable* patients. This conditional power will be calculated using formula (6) in Mehta and Pocock (2010) under the assumption that the interim estimate of the risk difference is the true population risk difference. The study will not be stopped for overwhelming efficacy or futility at this interim stage. Based on Table 1 of Mehta and Pocock (2010), if the $CP \leq 36\%$ or $CP \geq 90\%$, the study will continue to its original planned sample size of 92 evaluable subjects (120 enrolled subjects). Otherwise if $36\% < CP < 90\%$ (the Mehta and Pocock “promising zone”), then the sample size may be increased up to 240 enrolled subjects (~184 evaluable patients) in order to obtain enough evaluable subjects to yield up to 90% CP for the primary analysis (if the maximum increase to 240 enrolled patients does not yield 90% CP, the sample size may still be increased to 240 to maximize CP, at the recommendation of the independent DMB). This approach to sample size increase does not inflate the overall Type I error.

The sponsor and investigators will remain blinded to the interim results for the duration of the ongoing study. After the interim analysis is carried out, the recommendation made by the DMB to the sponsor will only be to keep sample size as is or to increase enrolled sample size to a given value; the reason for the recommendation will not be given to the sponsor.

OTHER STUDY PARAMETERS AND ANALYSES

The following will be carried out for the ITT and PP analysis populations unless otherwise specified.

A. Subject Disposition

The number and percentage of subjects in each population will be presented by treatment group. The number and percentage of subjects in each of the ITT and PP populations who prematurely discontinued prior to Week 6 will be presented overall and by reason of discontinuation within each treatment group. The number and percentage of ITT and PP subjects will be presented by investigative center within each treatment group.

The number and percentage of ITT and PP subjects entering the open-label phase will be presented overall and by original double-blind treatment group.

B. Baseline Demographics

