The primary hypothesis in the double-blind phase will be tested using Fisher's Exact test on the ITT and PP analysis populations. For the ITT population, there may be missing data at Week 6 due to, for example, patients prematurely withdrawing from the study. The first analyses for the ITT population will use available data. As a supportive sensitivity analysis, multiple imputation will be used to assess the robustness of the primary endpoint findings relative to missing data. Specifically, multiple imputation using the linear regression approach will be used to impute missing HAM-D¹⁷ across visits via SAS PROC MI; included as covariates in the linear model will be age, sex, race, education level, HAM-D17 measured at previous visits, investigative center, baseline MMSE, baseline IDS-SR, baseline C-SSRS, and ATHQ categorizations. Ten complete datasets will be created (the linear regression approach to multiple imputation assumes monotone missing data pattern; if such a pattern does not exist, then prior to each of the 10 linear regression imputations, any non-monotone missing data will first be imputed via the Monte-Carlo Markov Chain approach to create a monotone missing data pattern). Once 10 complete HAM-D¹⁷ datasets are generated, the determination of whether the patient achieved imputed clinical response at Week 6 will be calculated for each patient with missing data within each imputed dataset. The z-test for proportions with continuity correction (which yields very similar results to Fisher's Exact test) will then be applied to each of these 10 datasets to compare treatments on

the incidence of Week 6 clinical response. The numerator and denominator of the 10 continuity-corrected z -statistics will then be combined into a single continuity-corrected z-statistic using SAS PROC MIANALYZE. The resulting p-value from this z-statistic, assessing overall significance of treatment difference on clinical response rate at Week 6, will be calculated.

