In addition, a tipping point analysis will be performed to assess the likelihood that the observed significance would no longer hold based on various assumed values of the missing clinical response data. Specifically, to start, at Week 6, all missing data will be assumed to be successes for both the sTMS and sham groups. Fisher's exact test will then be run comparing treatments on this imputed clinical response rate and the treatment comparison Week 6 p-value will be generated. Then, the analyses will be repeated where 1 missing sTMS patient is assumed to be a failure, and all remaining sTMS and all Sham patients are assumed to be successes. Then the analyses will be repeated where 2 missing sTMS patients are assumed to be a failure, and all remaining sTMS and all Sham patients are assumed to be successes. This process will continue until the "tipping point" is reached. The "tipping point" is the imputation point at which the Fisher's Exact test p-value changes from significance to non-significance.

The above process will then be repeated but where 1 missing Sham patient is assumed to be a failure throughout the above one-failure-at-a-time imputation for sTMS patients. It will then be repeated but where 2 missing Sham patients are assumed to be a failure throughout the imputations for sTMS patients, etc.

G. Subgroup Analyses

The robustness of the primary efficacy outcome will be confirmed via subgroup analyses. Subgroups of subjects will be identified according to their investigative center, gender, age (<median, ≥median), education, concomitant medication, ATHQ history and duration of illness (<median, ≥median). The Fisher's Exact test on the primary endpoint analysis will be repeated within the subgroups of subjects defined by levels of the variable (e.g. adults < median age, adults ≥ median age). The purpose of this subgroup analysis is not to find significant treatment effect within subgroups, but rather to assess consistency of treatment effect across subgroups. This will be performed on the ITT population with available data and imputed data, and on the PP analysis population.

H. Secondary Analyses for Label Considerations

The following analyses will be conducted for the ITT (available and imputed data) and PP populations.

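### The primary Fisher exact test is valid and meets its stated power, but it is conservative; Boschloo's exact test would recover some power with fixed-sample size still at or below 5%

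*SAP*

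**What the plan says.** The SAP (Analysis of Primary Efficacy Endpoint) and Protocol 11.5 specify the same primary test on the PP population: "The test of the null hypothesis will be based on Fisher's exact test at a two-sided 0.05 level of significance". The sample size rests on that test. Protocol 11.4 and the SAP's Sample Size section give 81% power with 46 evaluable subjects per arm, for response rates of 34% on sTMS and 8% on sham.

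On losses, the SAP expects that "approximately 23% of enrolled subjects may not be part of the PP population in each treatment group", which is why 120 are enrolled to obtain 92.

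On centre, Protocol 5.3 says "Randomization will be stratified by site in blocks of 10 determined by a computer generated randomization table", and the SAP's Randomization section repeats the stratification. For analysis, "Sites with fewer than 10 subjects in the PP group will be pooled with other centers by geographic region", with pooling completed before the blind is broken. In the double-blind analysis of the primary endpoint, centre is used for the Breslow-Day interaction check, the subgroup summaries and the imputation model. It is not used in the primary test.

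Two sensitivity analyses in SAP section F are tied to Fisher's test. The multiple-imputation analysis uses a continuity-corrected z-test, justified by its closeness to Fisher. For the tipping-point analysis, "Fisher's exact test will then be run comparing treatments on this imputed clinical response rate".

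**The concern.** Fisher's test conditions on the total number of responders. With about 46 per arm, only a few tables are possible for each total, so the largest attainable level at or below 5% is often well below it. Some power is then given up without any gain in validity.

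This matters most where the trial is least secure. The sponsor adds an adaptive step because the sham rate and treatment difference are uncertain, and cites a minimum differential of 12 points. At the design effect there is power to spare; at a smaller effect a few points count for more.

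**Working it through.** **1. The plan's own figure.** Inputs from the SAP's Sample Size section: rates 0.34 and 0.08, n = 46 per arm, two-sided 0.05. So Δ = 0.26 and the mean rate is 0.21. The continuity-corrected normal formula is

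power = Φ{[Δ − 1/n − 1.96√(2 × 0.21 × 0.79/n)] / √[(0.34 × 0.66 + 0.08 × 0.92)/n]}

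= Φ{(0.2600 − 0.0217 − 0.1665)/0.0805} = Φ(0.892) = 81.4%.

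The stated 81% reproduces. Summing exact binomial probabilities over every table that Fisher's test rejects gives 83.6%. The plan is slightly pessimistic about its own test.

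**2. Fisher's true size.** For a common rate p, size(p) = ΣΣ Bin(a; n_A, p) Bin(b; n_S, p) × 1{Fisher P(a,b) ≤ 0.05}, maximised over p. The maximum is 3.0% at 46/46, 3.8% at 45/47 and 3.9% at 44/48.

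PP exclusions happen after randomisation, so equal arms are unlikely. If each of 60 per arm is retained independently with probability 92/120, the chance of exactly 46/46 is 1.5%. Over the splits that arise, Fisher's maximum size has median 4.0% (5th to 95th percentile 3.2% to 4.4%).

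**3. Boschloo's test.** Use the Fisher P value as the statistic, and reject when it is at or below the largest cut-off c for which the maximum of size(p) stays at or below 5%. Because c is never below 0.05, the test rejects whenever Fisher does. Exact enumeration gives c of about 0.075 at 46/46 and 0.059 at 45/47 and 44/48. Gains are taken before rounding.

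| Active/sham | Max size, Fisher | Max size, Boschloo | Power at 34% v 8%, Fisher → Boschloo | Power at 30% v 10%, Fisher → Boschloo |
|---|---|---|---|---|
| 46/46 | 3.0% | 4.7% | 83.6 → 88.7 (+5.1) | 58.9 → 67.5 (+8.7) |
| 45/47 | 3.8% | 4.9% | 87.7 → 88.6 (+0.8) | 65.8 → 67.4 (+1.5) |
| 47/45 | 3.8% | 4.9% | 85.9 → 87.8 (+1.9) | 62.4 → 65.8 (+3.3) |
| 44/48 | 3.9% | 4.9% | 86.5 → 87.8 (+1.3) | 63.7 → 66.0 (+2.3) |
| 48/44 | 3.9% | 4.9% | 86.6 → 89.1 (+2.5) | 63.7 → 68.2 (+4.5) |
| 92/92 | 3.6% | 5.0% | 99.3 → 99.5 (+0.2) | 91.3 → 93.2 (+1.9) |

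Averaged over the random-retention splits at 34% versus 8%, Boschloo has 88.2% power against Fisher's 86.2%. The 30% versus 10% case is an assumed smaller effect, not a figure from the documents.

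**4. CMH by pooled centre.** The documents give neither site sizes, nor the number of pools, nor site variance, so these are assumed. The set-up was 120 randomised in blocks of 10 within 12 or 16 sites, 28 of 120 lost at random from PP, sites pooled to at least 10 PP subjects, and a site log-odds SD of 0 to 0.8.

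- At 34% versus 8%: Fisher 86–87%, uncorrected CMH 88–89%, gain 1.9 to 3.5 points.
- Null rejection: CMH 4.1–5.1%, Fisher 2.2–3.9%.
- CMH against an unstratified chi-square test: −1.6 to +0.2 points. Removing discreteness, not stratifying, produces the gain.

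A second set-up (6 to 15 equal sites, 3 to 7 pools, SD 0 to 1.0) gave gains of 2.0 to 3.7 points in most settings, and 4.9 with six large sites and SD 1. With a continuity correction, CMH fell to 82–85%, below Fisher.

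With the interim step modelled (standard current-trend conditional power, since the cited formula is not reproduced in the documents), the CMH gain at 34% versus 8% was 1.4 to 2.1 points.

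**The case against.** The strongest reply is that nothing is broken. Fisher's test holds its level, the sample size was planned for it, and its exact power exceeds the stated figure. A conservative, familiar test is a reasonable choice for a confirmatory trial, and the gain at the design effect is small. All of that stands, and it is why this is an item to consider rather than a correction.

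A reader might go further and infer that the primary test loses these points because it ignores the site strata, and that CMH should replace it. The documents and figures do not support that, for three reasons.

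- Stratifying adds little or no power unless site effects are large.
- The strata would not be the randomisation strata. Subjects are randomised by site, but the pools are regional groups formed from PP counts, which are known only after randomisation. The SAP gives the pooling rule but names no regions.
- CMH's size control is approximate. Simulated null rejection stays near 5%, but the unstratified chi-square test has an exact maximum of 6.1% at 46/46. With about six pools there are roughly eight sham subjects in each, so at an 8% sham rate many pools would have no sham responder.

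Nor does the SAP neglect centre: it plans an interaction check, subgroup summaries and an imputation model that include it. These objections count against CMH as the primary test. They do not count against Boschloo's test, which is exact and uses no strata.

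**Conclusion.** The point holds as a matter of efficiency. Fisher's test is valid and meets its planned power, but uses at most 3.0% of the 5% level at 46/46 and about 4% at likely unequal splits. Under 34% versus 8%, Boschloo's test gains about 5 points at 46/46 and about 1 to 2 at most unequal splits. Under 30% versus 10% the gains are about 9 and about 1.5 to 3. At 240 randomised under 34% versus 8% the gain is negligible.

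The 3.0% and 5-point figures need exactly equal arms, which is unlikely. The typical figures assume that PP loss is random at the SAP's 23% rate. Boschloo's 5% bound is a fixed-sample result for given arm sizes, with PP loss unrelated to outcome; it was not simulated with the interim step. The CMH figures also depend on assumed site sizes, pools and variance.

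The documents do not support reading this as an invalid test, an underpowered trial, or a loss of power caused by leaving out site.

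**What to change.** Before the interim analysis and before unblinding:

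1. Make Boschloo's exact unconditional test, two-sided 0.05, the primary test in Protocol 11.5 and in the SAP's Analysis of Primary Efficacy Endpoint.
2. Add a CMH test without continuity correction, stratified by the planned pooled centres, with a stratified risk difference and 95% CI, as a pre-specified supportive analysis. State that its size control is approximate.
3. Name the test consistently in Protocol 11.4, the SAP's Sample Size section and SAP section F. There, run the tipping-point analysis with the new primary test. For the multiple-imputation z-test, replace the justification by closeness to Fisher and say whether the continuity correction stays.
4. Show the change to the regulator, with which the sponsor already discussed the primary population.

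The cost is document wording, minor programming, somewhat more computation and a less familiar test. No extra subjects or data are needed.

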The following secondary measures are to be considered for labeling. They will be analyzed using the gatekeeper (sequential) strategy to control for multiple comparisons by pre-specifying the order of testing (Westfall and Krishen, 2001). If the primary analysis is significant, these outcomes will be tested in the order listed below, each at the 0.05 alpha level. Testing for label consideration will cease when the first outcome results in a two-sided p-value greater than 0.05.

- Change from Baseline on the HAM-D¹⁷ score at Week 6;
- Change from Baseline on the MADRS score at Week 6;
- Clinical response, defined by 50% or greater reduction on the MADRS total symptom score at Week 6.

Treatments will be compared on the mean change from baseline HAM-D¹⁷ and MADRS scores at Week 6 using analysis of covariance adjusting for the baseline value of the given endpoint. Treatment group comparisons on the proportion of subjects who achieve MADRS clinical response at Week 6 will be carried out using Fisher's Exact test. Tests of hypotheses will be two-sided.

Assessment of investigator center-by-treatment interaction will be carried out using Breslow-Day test for the MADRS clinical response at Week 6 and using analysis of covariance with the independent variables of treatment group, investigative center, and the treatment-by-investigative interaction for change from baseline in HAM-D¹⁷ and MADRS at Week 6. Again, a non-significant interaction (using a 0.15 level of significance) or a significant interaction deemed only quantitative in nature supports the pooling of results across centers for the analyses on these secondary endpoints.

Multiple imputation for the ITT population for each endpoint will be carried out using linear regression in a similar manner as for the primary endpoint. For MADRS clinical response, the overall significance of the difference between treatment groups across the imputed datasets will be carried out in the same manner as for the primary efficacy endpoint. For the mean change from baseline at Week 6 for each of HAM-D¹⁷ and MADRS, analysis of covariance comparing treatments adjusting for the baseline value of the endpoint will be carried on each imputed dataset with the results being combined across imputed datasets using PROC MIANALYZE to obtain one overall assessment of treatment difference on the mean endpoint, adjusting for baseline.

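### The imputation model behind the SAP's supportive ITT analysis omits randomised treatment, so under missing-at-random a true sTMS–sham difference is pulled modestly toward zero

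*SAP*

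**What the plan says.** SAP section F first tests Week 6 response in the ITT population on available data and then adds imputation: "As a supportive sensitivity analysis, multiple imputation will be used to assess the robustness of the primary endpoint findings relative to missing data". Missing HAM-D17 scores are filled in across visits by linear regression in PROC MI. The predictor list is specific: "included as covariates in the linear model will be age, sex, race, education level", HAM-D17 at earlier visits, and "investigative center, baseline MMSE, baseline IDS-SR, baseline C-SSRS, and ATHQ categorizations". Treatment is not listed, and nothing says the imputation is run separately by arm. The MCMC step that first makes the missing pattern monotone has no treatment term or by-arm statement either. Response is then derived in each of ten completed datasets, and the arms are compared by a pooled continuity-corrected z-test.

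The same model is used elsewhere:

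- **Section G (subgroups):** "This will be performed on the ITT population with available data and imputed data, and on the PP analysis population".
- **Section H (secondary endpoints):** "The following analyses will be conducted for the ITT (available and imputed data) and PP populations", and "Multiple imputation for the ITT population for each endpoint will be carried out using linear regression in a similar manner". The two mean-change endpoints are compared "using analysis of covariance adjusting for the baseline value of the given endpoint".

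The SAP names the PP population as primary, under both Per Protocol and Analysis of Primary Efficacy Endpoint. Its Sample Size section assumes that "approximately 23% of enrolled subjects may not be part of the PP population in each treatment group". The protocol describes no multiple imputation; in section 11.5 its main ITT analysis leaves missing data out.

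**The concern.** An imputation model should contain the variable whose effect the completed data will estimate. Here missing scores from both arms are drawn from one pooled regression. The baseline predictors are balanced between arms by randomisation and so cannot stand in for treatment. Only observed post-baseline HAM-D17 values carry any of the arm effect. If dropouts would have followed their own arm's course, imputed sTMS scores drift toward sham and imputed sham scores toward sTMS.

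The analysis exists to show whether the primary finding survives missing data. The primary PP population is expected to leave out nearly a quarter of those enrolled, so the ITT results are the natural check on that exclusion. A real effect could then look fragile for a purely technical reason, and the imputed subgroup and secondary results would be shrunk in the same way.

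**Working it through.** **1. The plan's own figures.** Enrolment: 92 / (1 − 0.23) = 119.5, rounded to 120, or 60 per arm. Power at 46 per arm for 34% vs 8%, by the continuity-corrected normal formula with pooled rate 0.21:

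(0.26 − 1/46 − 1.96·√(2·0.21·0.79/46)) / √((0.34·0.66 + 0.08·0.92)/46) = 0.0718 / 0.0805 = 0.89, which gives 81.4%.

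This reproduces the stated 81%. Exact enumeration of Fisher's test gives 83.6%. The planning inputs are sound.

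**2. Earliest dropout, by algebra.** Suppose a share m of each arm leaves before Week 1. With no post-baseline score and no treatment term, the dropouts in both arms are imputed the same expected response rate r. The estimated difference is

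[(1 − m)·pA + m·r] − [(1 − m)·pS + m·r] = (1 − m)·(pA − pS).

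At m = 0.23, 26 points become 20.0 (loss 6.0) and 12 points become 9.2 (loss 2.8). Simulation of this case gave losses of 6.1 and 2.8.

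**3. Dropout spread over visits, by simulation.**

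- From the documents: 60 per arm, ten imputations and the 50% response rule (SAP); baseline HAM-D17 of 21.0, SD 3.3 (Protocol 1.1, feasibility study), kept if at least 17; Week 6 change SDs of 7.33 and 4.74 (Protocol 1.1, prior non-naïve completers).
- Assumed: an alternative common SD of 6.5; rater noise SD 2; an effect growing linearly to Week 6; two symptom-path models (random walk, subject slope); monotone dropout, completely at random and equally likely at each visit; 10% or 23% missing.
- Runs: 1,500 per scenario; simulation standard error of the loss 0.05 to 0.14 point. The main runs used baseline and earlier HAM-D17 as predictors. The MCMC step was not simulated.

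Loss in the response difference, in percentage points:

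| True rates | Missing | As written | Treatment as covariate, equal SDs | Treatment as covariate, SDs 7.33/4.74 | By arm, HAM-D17 history only |
|---|---|---|---|---|---|
| 27% vs 15% | 10% | 0.5–0.9 | 0.0–0.3 | 0.6–0.7 | 0.0–0.5 |
| 27% vs 15% | 23% | 1.3–2.0 | 0.0–0.3 | 1.3–1.6 | 0.0–0.5 |
| 34% vs 8% | 10% | 1.1–1.7 | 0.0–0.3 | 0.5–0.7 | 0.0–0.5 |
| 34% vs 8% | 23% | 2.5–4.1 | 0.0–0.3 | 1.2–1.5 | 0.0–0.5 |

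The as-written column spans both SD assumptions. With an early effect and late dropout the loss fell to about 0.1–1.0 point.

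At 23% missing, the chance that the pooled test favours sTMS at p ≤ 0.05 is 14–16% as written against 17–23% with treatment as a covariate (27% vs 15%), and 76–85% against 84–91% (34% vs 8%; another set of runs gave 72–81% as written).

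**4. A second simulation** used AR(1) correlation 0.75, a common SD of 6 and 23.3% missing. The full-data, as-written and with-treatment differences were:

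- Missing at random: 21.8, 18.7 and 21.9 points (loss 3.1/21.8 = 14%).
- Completely at random: 22.2, 18.5 and 22.1 (loss 3.7/22.2 = 17%).
- All before Week 1: 21.7, 16.7 and 21.7 (loss 5.0/21.7 = 23%).

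With SDs near the prior study's, missing at random: 29.5, 24.7 and 27.8.

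**5. No true effect** (20% in both arms, equal SDs). Bias was 0.0. False positives favouring sTMS were 0.3–0.5% as written and 0.9–1.3% with treatment included.

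**6. HAM-D17 mean change by ANCOVA** on imputed ITT data, true difference 3.8. The loss was 0.2–0.3 HAM-D17 points at 10% missing and 0.4–0.6 at 23%, and 0.0 with treatment included.

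**The case against.** **It is supportive and conservative.** This stands. The analysis errs against the sponsor, and three other analyses bypass the model. It limits the severity but does not cure the defect: a robustness check biased toward zero cannot tell fragility from artefact.

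**The bias depends on the target.** If sTMS dropouts would revert to sham's mean course, a run at 34% vs 8% and 23% missing gives a different picture. With a common SD, the plan as written was off by 0.0 points and the covariate version overstated the difference by 3.5. With SDs of 7.33 and 4.74, the plan as written understated by 1.5 and the covariate version overstated by 1.0. So the conclusion is tied to missing-at-random. A reader might infer that the omission is a deliberate reference-based analysis. The SAP states no such target, the pooled model also moves sham dropouts toward sTMS, and the tipping-point analysis already covers departures from missing-at-random.

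**The planning rates are PP rates, while imputation is used only in ITT.** This stands. The prior non-naïve ITT rates, 27% vs 15%, are the closer match, and there the test usually fails with or without treatment in the model.

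**The simple fix can recover little.** This stands in part. At 27% vs 15% with the prior study's SDs, one run lost 2.1 points as written and 1.8 with the covariate, because one pooled residual variance is still applied to both arms.

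**Conclusion.** The omission is real and its direction is clear under missing-at-random. With 10% to 23% missing and dropout spread over visits, the imputed ITT difference is understated by about 0.5 to 2 points at 27% vs 15% and about 1 to 4 points at 34% vs 8%. The loss is larger with very early dropout and smaller with late dropout. The missing rates, symptom paths and dropout pattern are assumptions. Severity is minor to should-fix.

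Three stronger readings are not supported:

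- **Losses near 6 points from a third of subjects missing.** The prior trial had 202 − 135 = 67 non-completers of 202. That trial included treatment-naïve subjects, and its completer definition also required 24 of 30 treatments, so this is not a missing-assessment rate. Here a missing Week 6 HAM-D17 is itself a PP exclusion, so the SAP's 23% non-PP share is the ceiling on its planning figure, though not on what may happen.
- **The label claims are compromised.** Section H opens the sequence on the primary analysis, which the SAP places in PP, and Protocol 11.5 marks PP as primary for these endpoints. PP has no missing Week 6 HAM-D17. Section H does not name the governing population outright, so the gate is probably, not certainly, unaffected.
- **No likelihood-based ITT analysis remains.** Protocol 11.5 specifies an MMRM with treatment terms where the SAP uses ANCOVA. The documents do not say the MMRM is withdrawn, so this point does not rest on its absence.

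**What to change.** Before unblinding, add randomised treatment as a covariate to every PROC MI step, both the regression and the MCMC step, for the primary, subgroup and secondary imputations. This needs one clause in SAP section F, carried into sections G and H, and one variable in the code. It needs no subjects or new data. The imputed ITT analysis becomes slightly less conservative.

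If arm SDs differ as in the prior study, about 1 to 2 points of bias remain at 23% missing. An optional further check is to impute by arm with a shorter list (baseline and earlier HAM-D17), which lost 0.5 point or less in the runs. The shorter list matters: with 22 added columns standing in for the full list, neither approach was uniformly better. Dropped covariates that predict outcome or dropout were not simulated, so shortening the list may carry a cost of its own.
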